#### **1.6 Description of the Trial Population**

The study population will be minimally 1 patient and maximally 6 patients above the age of 18 with PNH and known resistance to eculizumab. Patients may be male or non-pregnant females using adequate methods of contraception if of childbearing potential.

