All patients will return to the hospital out patient clinic for follow-up at a minimum of monthly intervals according to the schedule in appendix 1.

Blood and urine samples will be taken from all patients according the schedule on appendix 1.

Patients who have satisfactorily mastered the technique of self-administration of Coversin may be discharged home when considered appropriate to do so by the PI providing that adequate arrangements for daily pre-dose blood sampling and sample handling for CH50 samples have been arranged (see below).

All patients will be followed up at a minimum of monthly intervals by the PI. If at the 6 month follow-up the patient wishes to continue Coversin treatment and if the PI is satisfied as to the suitability of Coversin treatment, the patient may be transferred to the long-term follow-up protocol.

It is expected that the majority of patients will respond to an ablating dose of 0.57mg/kg followed by a daily maintenance dose of 25% of the ablating dose.

On a per patient basis this will be adjusted as necessary on the basis of clinical response and CH50 assay. The protocol allows for a flexible, tailored dose adaptation on day 7 and any subsequent follow-up. in patients who are not adequately controlled as is outlined below ..

If patients are not adequately controlled at the first (7 day) or subsequent follow up either of three options may be followed:

Patient will be reinduced with an identical ablating dose (0.57 mg/kg) and /or the maintenance dose may be increased with one step at the time for a maximum of 2

times according to the below schedule of increments . Each incremental dose level must be given for a minimum of 4 days.

The definition of adequately controlled coversin treatment is:

LDH <1.5xULN AND CH50 <10% of baseline.

It is expected that this adequate control is achieved at day 5.

If a recent CH50 result is not available at the time of assessment then the PI will make a decision on clinical grounds alone on the adequacy or otherwise of disease control.

If adequate control is not achieved on day 5 of maintenance therapy at the standard dose level (and day 5 of increment dose levels if applicable) the following dose adaptation will take place:

- If CH50  $\leq 10\%$  and LDH is reducing but still  $\geq 1.5xULN$ , treatment at the same maintenance dose level is continued for another week.

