- If LDH is decreasing and if CH50 is between 50 and 10% of baseline, the maintenance dose may be increased according to the schedule of increments of maintenance dose shown below.
- If LDH is not reducing and CH50 is >50% of baseline the patient must either be discontinued from the trial and switched to alternative therapy or must be readmitted to hospital for dose stabilisation following another ablating dose (0.57mg/kg) of Coversin. In either case the findings and course of action must be discussed by a Trial Steering Committee comprised of, at minimum, the PI, and the Medical Director of the Sponsor company.

The schedule of increments for the maintenance dose is as follows:

Ablating dose	First maintenance	Second mainte-	Third mainte-
	dose level	nance dose level	nance dose level
0.57 mg/kg	0.14 mg/kg	0.29 mg/kg	0.57 mg/kg

Within each patient the first incremented maintenance dose should be given at 24 hour intervals for at least 4 days until steady state is reached and at that point a CH50 assay should be performed. If the CH50 is not  $\leq 10\%$  of baseline (adjusted to 100%) then the next incremental dose (Second maintenance dose level should be given for at least another 4 days before switching to the Third maintenance dose level. If at any

stage the CH50 is >50% of baseline another ablating dose should be given before using the next incremental dose.

[figure not shown]
Blood samples and timing is shown in Appendix 1. Samples for CH50, antibodies and drug level should be processed as shown in Section 20 and sent to the Akari Therapeutics Plc complement laboratory for assaying. All other laboratory tests should be done locally in the PI's hospital laboratory.

If an ablating dose is repeated , PK/PD and other assessment will be performed as indicated in Appendix 1 at 1hr, day 2 and day 5.

At increments of the maintenance dose PK and PD and other assessments are repeated at day 5 as indicated in Appendix 1.

Extra samples for PK/PD may be taken at the discretion of the investigators during illness or infection.

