#### 6.1 Endpoints

Primary Efficacy Endpoint:

• Significant reduction in mean serum LDH from Day 0 (pre-dose) to Day 28 (AUC)

Secondary Efficacy Endpoints:

- Change in LDH from Day 0 (pre-dose) at monthly intervals after Day 28
- Change in proportion of PNH clone Day 0 Day 90
- Change in mean Hb Day 0 Day 90
- Change in mean Hp Day 0 Day 90
- Change in FACIT score Day 0 day 28- Day 90 Day 180
- Change in EORTC QLQ C30 score Day 0 -Day 28-Day 90 Day 180

Safety Endpoints:

- Frequency, type and relationship to treatment of AEs and SAEs
- Out of range laboratory parameters (haematology and chemistry)
- Vital signs
- ECG abnormalities Day 0 Day 90

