#### **13 STATISTICS**

#### **13.1** Statistical Methods

The statistical approach taken will depend on the number of patients recruited.

If less than 4 patients are recruited, each patient will be analysed separately. Changes in the primary efficacy outcome during the period Day 0 to Day 28 will be analysed using linear regression using all measurements in the analysis. Secondary efficacy outcomes measured multiple times will be analysed in an equivalent manner.

If 4 or more patients are recruited, the patients will be analysed as a single group. Differences between specific timepoints (e.g. Day 0 and Day 28) for the primary and secondary efficacy endpoints will be performed using the paired t-test.

Additionally the change in the primary efficacy outcome over time will also be examined using all measurements. Mixed model will be used to allow for repeat measurements from the same patients, with the patient considered as a random effect.

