#### **13.3** Significance Level

For all comparisons p < 0.05 will be considered significant.

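### With one to three patients, the per-patient LDH regression has no within-patient error structure, so its p < 0.05 rule runs above 5% if closely spaced values are correlated

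*Combined protocol and SAP*

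**What the plan says.** Section 1.6 sets the size of the trial: "The study population will be minimally 1 patient and maximally 6 patients above the age of 18". Section 13.1 makes the method depend on how many are recruited: "If less than 4 patients are recruited, each patient will be analysed separately". In that case the primary efficacy outcome over Day 0 to Day 28 "will be analysed using linear regression using all measurements in the analysis", and secondary outcomes measured repeatedly are handled the same way. No error structure, robust variance or autocorrelation term is named.

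Repeat measurements are mentioned only after the rule for four or more patients: "Mixed model will be used to allow for repeat measurements from the same patients, with the patient considered as a random effect".

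Section 13.3 covers everything: "For all comparisons p < 0.05 will be considered significant". Section 6.1 words the primary efficacy endpoint as "Significant reduction in mean serum LDH from Day 0 (pre-dose) to Day 28 (AUC)". Section 3.1 defines it differently, as the LDH AUC over Day 0-28 compared with the 28 days before treatment. The synopsis lists only descriptive methods.

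On sampling, section 6.0 says "Blood samples and timing is shown in Appendix 1". That appendix is not in the supplied text.

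**The concern.** A linear regression with no further qualification takes the residuals as independent. Successive LDH values from one patient, a day or a few days apart, are unlikely to meet that assumption. With positive serial correlation, a series carries less information about its slope than its number of points suggests. The usual standard error is then too small and the p-value too optimistic.

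One to three patients is an explicitly planned outcome. The trial is open label with no comparator, and section 6.1 builds significance into the primary efficacy endpoint. A claim of efficacy in this case would therefore rest on a test whose real error rate is not the stated 5%.

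**Working it through.** **Inputs from the documents.** Significance level 0.05 (13.3). Per-patient linear regression on all Day 0-28 values (13.1). One to three patients for this branch (13.1, 1.6). Sidedness is not stated.

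**Inputs not in the documents, so assumed.** LDH sampling days: a range from four values to daily. Within-patient correlation: AR(1), corr(y_i, y_j) = ρ^|t_i − t_j| with t in days, main range ρ = 0.5 to 0.9. Two-sided test.

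**Test.** With S = Σ(t − t̄)², slope b = Σ(t − t̄)y / S and s² = RSS/(n − 2), reject if |b| / √(s²/S) exceeds the 97.5% point of t on n − 2 degrees of freedom. Series were simulated with no trend, 100,000 per cell (20,000 for the Days 0, 5, 7, 28 row). The Monte Carlo standard error is at most √(0.25/100,000) = 0.16 percentage points, or √(0.25/20,000) = 0.35 for that row.

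**Step 1: the nominal figure.** With independent errors (ρ = 0) the test rejects 4.9-5.1% of the time on every schedule in the table, which reproduces the stated 5%.

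**Step 2: correlated errors, no true trend.** Two-sided false-positive rate:

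| Assumed LDH schedule (values) | ρ = 0.5 | ρ = 0.7 | ρ = 0.9 |
|---|---|---|---|
| Weekly (5) | 5.1% | 6.0% | 12.2% |
| Days 0, 5, 7, 28 (4) | 5.6% | 7.1% | 14.0% |
| Twice weekly (9) | 6.7% | 11.5% | 30.3% |
| Days 0, 1, 2, 5, 7, 14, 21, 28 (8) | 9.4% | 14.8% | 32.3% |
| Daily to Day 7, then weekly (11) | 11.7% | 20.1% | 41.5% |
| Every 2 days (15) | 11.7% | 22.6% | 46.9% |
| Daily (29) | 24.9% | 40.4% | 62.6% |

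Spacing matters as much as ρ. At weekly spacing the correlation between neighbouring values is ρ^7: 0.5^7 = 0.008, 0.7^7 = 0.08 and 0.9^7 = 0.48. Weekly values are therefore nearly independent unless ρ is high.

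**Step 3: direction.** Under no effect the slope is symmetric about zero, so half of the false positives are rises. False reductions at ρ = 0.5 to 0.9, against 2.5%:
- weekly: 5.1/2 = 2.6% to 12.2/2 = 6.1%
- eight visits: 9.4/2 = 4.7% to 32.3/2 = 16.2%
- daily: 24.9/2 = 12.5% to 62.6/2 = 31.3%

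**Step 4: does modelling the correlation cure it?** Generalised least squares with the true ρ gives 4.9-5.2%. In practice ρ must be estimated from the same short series. A REML fit with AR(1) errors still rejects 5.5% / 7.9% / 15.3% (eight visits) and 8.4% / 11.1% / 18.2% (daily) at ρ = 0.5 / 0.7 / 0.9. A nominal 95% interval would then cover about 85-94.5% and 82-92% of the time respectively.

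**Step 5: the larger-sample branch.** A random patient effect gives any two values from one patient the same correlation, however far apart they are. It does not model correlation that fades with time, so the mixed model as described would not remove this problem either.

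**The case against.** The strongest reply is that the size of the effect is not a property of this plan, because the supplied text gives neither the LDH schedule nor the correlation. That stands. A reader might infer from the table that the false-positive rate is somewhere from 9% to 63% whatever the schedule. The documents do not support that. Weekly LDH with ρ of 0.5 to 0.7 shows almost no inflation, so 9% is not a floor. The 63% end needs 29 daily LDH values and ρ = 0.9, and daily sampling is mentioned only for another assay: "adequate arrangements for daily pre-dose blood sampling and sample handling for CH50 samples have been arranged". Section 6.0 does bring patients back daily until the dose is stable and uses LDH in decisions around days 5 and 7. Some early clustering is therefore a fair assumption, but daily LDH to Day 28 is not shown.

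A reader might also take the two-sided rates as the chance of a false claim of benefit. Only about half are reductions. Compounding the rates over three patients would add a multiplicity problem, which is a separate matter. A real fall in LDH from a non-drug cause is confounding in an uncontrolled design, and no choice of error structure removes it.

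Finally, the synopsis promises only descriptive methods, section 13.5 calls this mainly a safety study, and section 13.1 never says the errors are independent. It is fair to call this under-specification. It does not dispose of the point, because 13.3 applies the threshold to every comparison and 6.1 puts significance into the primary efficacy endpoint.

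**Conclusion.** The point holds. As written, the one-to-three-patient analysis gives a p-value that is too small whenever LDH values close in time are positively correlated, and nothing in section 13 allows for this. Under assumed AR(1) correlation of 0.5 to 0.9, the two-sided rate is about 5-12% with weekly LDH, 9-32% with eight visits clustered early, and 25-63% only with daily LDH to Day 28. Confidence in the defect is high. Confidence in its size is moderate, because both the schedule and the correlation are assumptions. The plan should be changed, although nothing in the supplied text makes a go/no-go decision depend on this p-value.

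**What to change.** In section 13.1, for fewer than four patients, remove the regression p-value and state that the 13.3 threshold does not apply. Report each patient's time-weighted mean LDH (AUC divided by time) over Day 0-28 against the same quantity for the 28 days before treatment, with the full series plotted. This follows the synopsis and the section 3.1 endpoint, which a slope over Day 0-28 does not test. Bring the wording of 6.1 into line for this case.

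If a model-based interval is shown, use continuous-time AR(1) errors, label it descriptive, and say that it still under-covers in one short series (rejection about 5.5-15% with eight visits, 8-18% with daily values, on the assumptions above). For four or more patients, do not rely on the random patient effect alone to handle day-to-day correlation.

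The change is to wording. It needs no patients or visits beyond what section 3.1 already implies, including its pre-treatment LDH values. The cost is the loss of a nominal significance claim when one to three patients are recruited.

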#### 3.1 Endpoints

Safety:

- Frequency, type and relationship to treatment of AEs and SAEs
- Out of range laboratory parameters (haematology and chemistry)
- Vital signs
- ECG abnormalities Day 0 Day 90

Primary efficacy endpoint:

• Serum lactic dehydrogenase (LDH) AUC from Day 0 to Day 28 compared with 28 days pre-treatment

Secondary efficacy endpoints:

- Haemoglobin at Day 28 and day 90 and Day 180, absolute and change from baseline
- LDH at days 90 and 180
- Haptoglobin at day 28, day 90 and day 180, absolute and change from baseline
- Dependency on blood transfusion
- Quality of Life at days assessed by the FACIT and EORTC QL-C30 instruments compared to Day 0, day 28, 90 and 180

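### With fewer than four patients, the per-patient regression test of FACIT and EORTC QLQ-C30 turns on the shape of the response, not its size: full benefit by Day 28 that then holds gives p = 0.377 however large it is

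*Combined protocol and SAP*

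**What the plan says.** Section 13.1 makes the method depend on enrolment: "If less than 4 patients are recruited, each patient will be analysed separately". In that branch the primary outcome, over Day 0 to Day 28, "will be analysed using linear regression using all measurements in the analysis". For the secondary outcomes the instruction is: "Secondary efficacy outcomes measured multiple times will be analysed in an equivalent manner". Section 13.3 adds: "For all comparisons p < 0.05 will be considered significant".

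The assessment days for fatigue and quality of life agree in both endpoint lists. Section 3.1 has: "Quality of Life at days assessed by the FACIT and EORTC QL-C30 instruments compared to Day 0, day 28, 90 and 180". Section 6.1 has: "Change in FACIT score Day 0 day 28- Day 90 Day 180" and "Change in EORTC QLQ C30 score Day 0 -Day 28-Day 90 Day 180".

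Enrolment is planned at one to six patients (synopsis, sections 1.6 and 6.0), so the branch for fewer than four is a foreseen case. Section 13.1 does not name the regressor, its scale or any transformation of time, and section 13.3 does not say whether tests are one- or two-sided. The statistical methods entry in the synopsis mentions descriptive statistics only, which does not match the tests in section 13.

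**The concern.** Four values per patient leave 2 residual degrees of freedom, so a straight line on day must fit almost perfectly to reach p < 0.05. If a patient improves early and stays improved, the profile is a step. A straight line fits a step badly, and least squares counts the misfit as residual error. A larger step enlarges that error in the same proportion as the slope, so the t statistic does not move.

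At stake is the reading of the fatigue and quality-of-life results in a trial of one to three patients. A complete, durable, early responder would be labelled not significant on FACIT and EORTC QLQ-C30, while a patient with a smaller but steadily rising score could be labelled significant.

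**Working it through.** The plan states no power, p-value or sample-size figure for these tests, so there is nothing of its own to reproduce.

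**Inputs from the documents.** Assessment days x = (0, 28, 90, 180), sections 3.1 and 6.1. Linear regression within each patient, section 13.1. Threshold 0.05, section 13.3.

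**Assumptions.** Calendar day, untransformed, is the regressor, and the test is two-sided.

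**Critical value.** The test is t = r·√(2/(1 − r²)) on 2 df. On 2 df the two-sided p-value equals 1 − |r|, so p < 0.05 requires |r| > 0.950 (|t| > 4.303).

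**Noise-free step of size d, y = (b, b+d, b+d, b+d).**
- Mean day = (0 + 28 + 90 + 180)/4 = 74.5.
- Sxx = 784 + 8,100 + 32,400 − 4 × 74.5² = 41,284 − 22,201 = 19,083.
- Sxy = d(298 − 4 × 74.5 × 0.75) = 74.5d.
- Syy = d²(3 − 4 × 0.75²) = 0.75d².
- r = 74.5/√(19,083 × 0.75) = 74.5/119.63 = 0.623. Both b and d cancel.
- t = 1.126 and p = 1 − 0.623 = 0.377. The one-sided p is 0.189.

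**Other noise-free shapes on the same four days** (values as fractions of the final benefit):

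| Day 0, 28, 90, 180 | r | p |
|---|---|---|
| 0, 1, 1, 1 | 0.623 | 0.377 |
| 0, 0.8, 1, 1 | 0.736 | 0.264 |
| 0, 0.5, 1, 1 | 0.853 | 0.147 |
| 0, 0.3, 0.7, 1 | 0.973 | 0.027 |
| exactly linear in day | 1 | 0 |

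For an exponential approach to the final level, p is 0.166 with a time constant of 30 days, 0.067 with 60 days and 0.034 with 90 days.

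**Other choices of regressor, noise-free step.** Visit number gives p = 0.225 and log(day + 1) gives p = 0.055. Neither reaches 0.05.

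**Power with independent unit-SD noise** (simulation, two-sided 5%). The linear shape reaches its full size at Day 180. The indicator test replaces day with a 0/1 regressor for pre-dose versus on treatment.

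| Benefit | Step shape, slope on day | Step shape, indicator | Linear shape, slope on day | Linear shape, indicator |
|---|---|---|---|---|
| 1 SD | 5.1% | 8% | 8% | 5% |
| 3 SD | 2.9% | 32% | 26% | 3.4% |
| 5 SD | 0.4% | 62% | 54% | 0.8% |
| 10 SD | about 0% | 98% | 95% | about 0% |

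Both tests hold 5% when there is no effect. Each loses power with growing benefit under the shape that it does not model. The symmetry is exact without noise: the correlation between day and the indicator is the same 0.623, so a perfectly linear improvement tested with the indicator also gives p = 0.377.

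**If the Day 0 to Day 28 window also carries over.** Each score would then have two values and no residual degrees of freedom, so no test could be done.

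**The case against.** The strongest reply concerns shape. A reader might infer that any sustained improvement fails this test. The documents do not support that, because the table above includes noise-free improvements that reach significance. Nor do they show that these scores will follow a step. Section 6.0 expects adequate control by Day 5, but defines control by LDH and CH50 only. No section gives a time course for FACIT or EORTC QLQ-C30, and assessments at Days 90 and 180 allow for later change. This stands, and it limits the claim to dependence on shape.

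A reader might also extend the p = 0.38 result to haemoglobin and haptoglobin. Section 3.1 lists them at Days 28, 90 and 180, but section 13.1 uses every measurement and the sampling schedule is in Appendix 1, which is not in the text available. A noise-free step gives p = 0.148 on assumed monthly visits and 0.301 on weekly-then-monthly visits. If pre-treatment values are assumed at Days −28, −14 and 0 with roughly monthly visits after, it gives p = 0.011. These outcomes may be affected, but that cannot be settled here.

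The regressor is an inference. Day is the natural reading, but an on-treatment indicator would also be a linear regression. That is a gap in the plan and does not rescue it, since either choice fails for one plausible shape.

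Finally, the study is mainly about safety, these outcomes are secondary, and no stopping, dosing or continuation rule uses their p-values. That is a fair argument about severity.

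**Conclusion.** The point holds for FACIT and EORTC QLQ-C30 when fewer than four patients enrol. With day as regressor and a two-sided test, full benefit by Day 28 that then holds gives p = 0.377 at any size. Having 80% of the benefit by Day 28 gives 0.26, and 50% gives 0.15 (full benefit by Day 90 in both). Under the step shape, power starts near the 5% error rate and falls towards zero as benefit grows. Slow, near-linear improvement can reach significance. The label therefore reflects the shape of a patient's response rather than its size, and the documents give no basis for assuming one shape.

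Severity is should-fix. The primary LDH analysis is not at issue, and neither is the branch with four or more patients, where a paired t-test between time points is planned.

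**What to change.** In section 13.1, for fewer than four patients, replace the regression test for FACIT and EORTC QLQ-C30, and for any other secondary outcome with so few values, by a listing for each patient: the observed value at each assessment and the change from Day 0 at Days 28, 90 and 180, with no p-value and no statement of significance. Limit section 13.3 accordingly. This fits the way sections 3.1 and 6.1 already define these endpoints, agrees with the synopsis, and assumes no time course.

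Do not substitute a test on a pre-dose versus on-treatment indicator, because it fails in the same way when improvement is gradual.

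The cost is wording only: no visit, sample or treatment changes. The downside is that these outcomes have no formal test in this branch, and each change from Day 0 rests on a single baseline value.

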#### **13.2** Number of Subjects

A total of 6 patients may be enrolled under this protocol if they present.

#### **13.3** Significance Level

For all comparisons p < 0.05 will be considered significant.

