## **Protocol synopsis**

	Exclusion Criteria:		
	• Pregnancy (females)		
	• Known allergy to ticks or severe reaction to arthropod venom (e.g. bee or wasp venom)		
	• Failure to satisfy the PI of fitness to participate for any other reason		
Treatment Regimen:	Single ablating dose of 0.57mg/kg per subject followed by daily maintenance doses. The initial maintenance dose will be 25% of the ablating dose. If this is insufficient to maintain complement activity at $\leq 10\%$ of baseline (pre-treatment) level after 5 days of treatment the daily maintenance dose will be increased by doubling until that level of inhibition is achieved. In the event of 100% inhibition being achieved the dose may be titrated downwards at the PI's discretion until a satisfactory clinical result is obtained. If at any point in treatment complement activity (CH50) is 50% of baseline or more a further ablating dose of 0.57mg/kg should be given. An increased daily maintenance dose may be required in the event of intercurrent infection or illness. CH50 level should be checked in the event of deteriorating clinical response manifested by rising serum LDH.		
Duration of Treatment:	Patients will undergo an initial period of 6 months treatment according to this protocol. At the expiry of this period, and on the recommendation of the PI, patients will have the option of remaining on long-term Coversin therapy and will enter the long term follow-up study.		
Endpoints:	Efficacy Endpoints:		
	Primary: Reduction in serum LDH from day 0 – Day 28		
	Secondary: Hb, haptoglobin, Fatigue (FACIT), Quality of Life (EORTC QL-C30), PNH RBC clone size, Transfusion requirement		
	Safety Endpoints:		
	Adverse events, ECG, Laboratory results, Vital signs.		
Statistical Methods:	Descriptive statistics		

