## 13.5 Deviations from the Statistical Plan

It is not envisaged that there should be any deviations from the statistical plan since this is primarily a safety study. Any unexpected deviations (eg a requirement for a trend analysis not foreseen in planning the trial) will be discussed with the PI and the statistical advisor and the rationale for such an analysis will be included in the trial report.

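### The synopsis promises descriptive statistics, but Section 13 tests primary and secondary efficacy endpoints at an unadjusted p < 0.05, so chance secondary findings can be labelled significant

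*Combined protocol and SAP*

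**What the plan says.** The Statistical Methods entry of the synopsis reads, in full, "Descriptive statistics".

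Section 13.1 sets out two alternative branches.

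- **Fewer than 4 patients:** each patient is analysed separately, with linear regression of the primary efficacy outcome over Day 0 to Day 28. In addition, "Secondary efficacy outcomes measured multiple times will be analysed in an equivalent manner".
- **4 or more patients:** "If 4 or more patients are recruited, the patients will be analysed as a single group". Differences between time points "for the primary and secondary efficacy endpoints will be performed using the paired t-test". A mixed model with patient as a random effect is added, for the primary outcome only.

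Section 13.2 sets the upper limit: "A total of 6 patients may be enrolled under this protocol if they present". Section 13.3 then says, without distinguishing primary from secondary, "For all comparisons p < 0.05 will be considered significant". Section 6.1 puts significance into the primary endpoint itself: "Significant reduction in mean serum LDH from Day 0 (pre-dose) to Day 28 (AUC". Section 13.5 remarks that "this is primarily a safety study".

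The synopsis and Sections 3.1 and 6.1 each name one primary efficacy endpoint and list the others as secondary. Section 13 has no multiplicity adjustment, testing order or exploratory label.

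**The concern.** The synopsis and Section 13 describe two different kinds of analysis. Someone who reads only the synopsis expects summaries and patient profiles. Someone who follows Section 13 will run a series of tests and call each one below 0.05 significant.

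In a trial of at most six patients with many endpoint/time combinations, that rule will often label a chance result significant. One quality-of-life visit at p = 0.04, for example, would qualify, with nothing in Section 13 telling the reader to treat it as exploratory. Section 19 says the results will be posted on a public registry, so the label would travel beyond the study report.

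The primary outcome has a related gap. With 4 or more patients it receives both a paired t-test and a mixed model, and the plan does not say which one decides.

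**Working it through.** The plan gives no power calculation, number of tests or family-wise error rate, so there is no derived figure to reproduce. The only stated number is the 0.05 threshold. It is taken as two-sided, because the plan does not state sidedness.

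**Step 1: count the tests in the branch with 4 or more patients.** Each endpoint/time pair is counted once.

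| Endpoint | Section 3.1 | Section 6.1 | Merged |
|---|---|---|---|
| LDH, primary | 1 | 1 | 1 |
| LDH, later | 2 (Days 90, 180) | 5 (monthly) | 5 |
| Haemoglobin | 3 | 1 | 3 |
| Haptoglobin | 3 | 1 | 3 |
| FACIT | 3 | 3 | 3 |
| EORTC | 3 | 3 | 3 |
| PNH clone | – | 1 | 1 |
| Transfusion | 1 | – | 1 |
| **Total** | **16** | **15** | **20** |

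Assumptions in the count:
- five monthly LDH visits between Day 28 and Day 180;
- one score per quality-of-life instrument;
- transfusion counted as one test, although no time point is given for it;
- absolute value and change from baseline counted together;
- every listed time point tested, although Section 13.1 gives Day 0 versus Day 28 only as an example.

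The mixed model on the primary would add one more test and is left out.

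**Step 2: independent tests.** If no endpoint truly changes, the chance of at least one p < 0.05 among m tests is 1 − 0.95^m.

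- m = 15: 1 − 0.95^15 = 0.537
- m = 16: 1 − 0.95^16 = 0.560
- m = 20: 1 − 0.95^20 = 0.642

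**Step 3: correlated tests.** The documents give no correlations, so a range is assumed. Two-sided paired t-tests were simulated with no true change, normal differences, n = 4, 5 and 6, and at least 40,000 replicates per setting. Ranges run over n.

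| Correlation within / between endpoints | 15 tests | 16 tests | 20 tests |
|---|---|---|---|
| 0.5 / 0.3 | 46–48% | 49–51% | 55–57% |
| 0.7 / 0.5 | 38–41% | 40–43% | 44–48% |
| 0.9 / 0.5 | 32–35% | 34–38% | 38–42% |
| 0.9 / 0.7 | 26–30% | 28–31% | 30–34% |

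**Step 4: fewer than 4 patients.** With three patients, one regression each on the primary, and each regression holding its nominal 5%, the chance of at least one significant patient is 1 − 0.95^3 = 0.143. Section 13.1 also applies the regression to repeated secondary outcomes, so 14% covers only part of what is planned.

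**Step 5: the primary alone.** One pre-named test has a 5% false-positive rate. The other tests do not change that.

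**The case against.** The strongest defence is that this is an open-label, non-comparative study of one to six patients in which efficacy is a secondary objective and Section 13.5 puts safety first. One primary efficacy endpoint is named and no confirmatory claim rests on any secondary. Formal multiplicity control would be out of proportion, and one sentence calling the secondary tests exploratory and unadjusted might be enough. Most of this stands: no adjustment is needed. What it does not answer is that Section 13.3 itself applies the word significant to all comparisons while the synopsis promises description, and no section reconciles the two.

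The size is also open to challenge. Twenty tests is the merger of two differing lists, not a number the plan states. Any lower bound depends on assumed correlations, and LDH, haemoglobin and haptoglobin are related measures repeated in the same patients. The figures also count false results in either direction. A false claim of benefit alone has a chance of 1 − 0.975^20 = 0.397 for 20 independent tests, and less under positive correlation if all endpoints are oriented alike. These points are accepted, and the range above is wide for that reason.

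A reader might infer more than the documents support:

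- *That Section 13.3 declares every comparison significant.* It only sets the threshold for calling one significant.
- *That regressions, t-tests and a mixed model are all run on all endpoints.* Regression and t-tests are alternatives chosen by patient number, and the mixed model is for the primary outcome only.
- *That the false-positive rate of the primary test is inflated.* A single primary test is not affected.
- *That secondaries formally rank with the primary.* The endpoint lists keep them apart; only the significance rule fails to.
- *That the error is at least 40%.* That floor rests on a particular assumed correlation and on the merged count.

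**Conclusion.** The concern holds as a conflict within the protocol: the synopsis says descriptive, while Section 13 prescribes tests with one unadjusted threshold for all comparisons. If Section 13 is followed with 4 to 6 patients, the chance of at least one nominally significant result when nothing has changed lies between about 26% (15 tests, correlation 0.9 within and 0.7 between endpoints) and 64% (20 independent tests). Even the low end is about five times the nominal 5%.

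This is an any-endpoint error rate. It rests on the counting assumptions above, two-sided tests and correlations that the documents do not supply. It bears on secondary results and on any reading of at least one significant finding, not on a single primary test. It warrants a wording change before analysis and does not undermine the design.

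**What to change.** Amend Section 13.3 so that, with 4 or more patients, p < 0.05 supports a significance statement for one named primary LDH analysis only. This requires two choices:

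1. Name either the paired comparison or the mixed model as the deciding analysis.
2. Settle on one LDH definition. Section 3.1 compares the Day 0 to Day 28 AUC with the 28 days before treatment, whereas the synopsis and Section 6.1 describe a reduction from Day 0 to Day 28. All three should then carry the same wording.

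Report the following as estimates with 95% confidence intervals and individual patient profiles: all secondary endpoints, all other time points, the primary analysis that was not chosen and, with fewer than 4 patients, every single-patient analysis. Any p-values shown there should be labelled nominal and exploratory. Change the synopsis entry to descriptive statistics plus the one named test.

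The cost is wording in the synopsis and Sections 3.1, 6.1, 13.1 and 13.3. The sponsor loses the significant label on secondary and single-patient results, and below 4 patients there is no significance statement at all. No visit, sample or treatment procedure changes.
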